### 6.4.6. Predictions: D2R and MOR

For D2R, testing for the main effect of group (obese vs. lean) as well as the interaction between group (obese vs. lean) and measurement (pre- vs. postoperative) will reveal whether lower  $D_2R$  availability – particularly in the striatum - in obesity will be reversible upon successful weight loss following surgery. For MOR, testing for the main effect of group (obese vs. lean) and an interaction

between group (obese vs. lean) and measurement (pre- vs. postoperative) will reveal whether obesity is associated with higher MOR availability – particularly in the striatum - , and whether this will be reversible upon successful weight loss following surgery. Additionally, self-reported trait craving for foods will be correlated with striatal MOR density. In line with the animal work (69,105), we predict that food craving will be positively associated with MOR availability in the striatum.

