## 4.2. Study design

Patient Group (will be studied pre and 6 months after the surgery):

Visits before Surgery	Examinations (table 1 and table 2 in the laboratory test)
Preliminary visit	Doctor's checkup Oral glucose tolerance test Visit to the PET and MRI scan
1. PET-visit	Calorimetry (fasting) Perfusion-PET PET-scan with 18F-FTHA -tracer
2. PET-visit MRI-visit	PET-scan with 11C-raclopride ja 11C-carfentanil tracers MRI-scan

Visits after Surgery	Examinations
Preliminary visit	Oral glucose tolerance test
1. PET-visit	Calorimetry (fasting) Perfusion-PET PET-scan with 18F-FTHA -tracer
2. PET-visit	PET-scan with 11C-raclopride and 11C-carfentanil tracers
MRI-visit	MRI-scan

Control group (will be studied only once expect brain fMRI):

Visit times	Examinations
Preliminary visit	Doctor's checkup Oral glucose tolerance test Blood samples
1. PET-scan	Calorimetry (fasting) Perfusion-PET PET-scan with 18F-FTHA -tracer
2. PET-visit	PET-scan with 11C-raclopride and 11C-carfentanil tracers
1. MRI-visit	MRI-scan
2. MRI-visit (after 6 months)	MRI-scan

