## 6. ASSESSMENTS

## 6.1 General study outline

**Patient Group:** (will be studied pre and 6 months after the surgery):

Visits before Surgery	Examinations
Preliminary visit	Doctor's checkup
	Oral glucose tolerance test
	Visit to the PET and MRI scan
1. PET-visit	Calarimetry (fasting)
	Perfusion-PET
	PET-scan with 18F-FTHA -tracer
2. PET-visit	PET-scan with 11C-raclopride and 11C-carfentanil tracer
MRI-visit	MRI-scan

Visits after Surgery	Examinations
Preliminary visit	Oral glucose tolerance test
1. PET-visit	Calorimetry (fasting) Perfusion-PET PET-scan with 18F-FTHA -tracer
2. PET-visit	PET-scan with 11C-raclopride and 11C-carfentanil tracer
MRI-visit	MRI-scan

Control group: (will be studied only once):

Visit times	Examinations
Preliminary visit	Doctor's checkup
	Oral glucose tolerance test
	Blood samples
1. PET-scan	Calorimetry (fasting)
	Perfusion-PET
	PET-scan with 18F-FTHA -tracer
2. PET-visit	PET-scan with 11C-raclopride ja 11C-carfentanil tracer
1. MRI-visit	MRI-scan
2. MRI-visit (after 6 months)	MRI-scan

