
reference region. Both ROI-based statistics and statistical parametric mapping (SPM) (84) will be used in the statistical analyses.

An integrated PET/CT, GE DiscoveryTM ST System (General Electric Medical Systems, Milwaukee, WI, USA) with resolution of 3.75 is used for PET studies. All data will be corrected for dead-time, decay and measured photon attenuation. Dynamic PET-scans will be reconstructed with MRP reconstruction method (85). Brain scan is performed with a covering the whole brain in 3D mode. CT scans will be conducted to correct for photon attenuation and to evaluate fat masses and tissue density(86) . Plasma radioactivity is measured with an automatic gamma counter (Wizard 1480 3", Wallac, Turku, Finland. Plasma glucose and free fatty acids are frequently measured during the PET study.

According to the study protocol the patients will get two FTHA, two raclopride and two carfentanil injections. These will result in 14.8 mSv of radiation dose. Moreover, the measurement from CT will result in 6.7 mSv of effective dose. Altogether the radiation dose to study subjects will be 22,5 mSv which equals to exposure to natural background radiation in Finland for 4 years and 4 months. Dosimetry calculations done by the hospital physicist can be found from the appendix. So in general, the total dose accounting all PET-studies for patients is less than 22.5 mSv and for control group less than 11.25 mSv.

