## 9. ETHICS

## 9.1. Ethical considerations

The studies will be performed using standard procedures that have been in clinical or research routine use for years in the Turku PET Centre. This study will be conducted according to Good Clinical Practice and the Declaration of Helsinki. Written informed consent for the study will be obtained from all subjects before the beginning of the study. Subjects will be informed of their right to withdraw from the study at any time. At least one medical doctor will be available at all times during the study. All necessary investigator contact information will be provided along with a description of the study. The radiation dose fof patients will be around 22.5 mSv which is approximately 4.4 times the natural background radiation in Finland for one years. Although there is no exact knowledge about the risk for developing cancer after this dose of radiation, the risk of fatal cancer is estimated to correspond to the risk for dying when driving 22500 kilometres in a car or smoking 225 cigarettes (109). As the control group is studied only once the radiotion dose will be around 11.25 mSv.

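### Reversibility of D2R and MOR is to be tested by a group-by-measurement interaction, but lean controls have receptor PET only once, so that interaction cannot be estimated

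*Protocol*

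**What the plan says.** **The test.** Section 6.4.6 plans, for D2R, a main effect of group and a second term: "the interaction between group (obese vs. lean) and measurement (pre- vs. postoperative) will reveal whether lower" D2R availability in obesity is reversible after successful weight loss. For MOR it plans the same two terms, the interaction being "between group (obese vs. lean) and measurement (pre- vs. postoperative) will reveal whether obesity is associated with higher MOR availability" and whether that is reversible.

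**The measurements.** Section 4.2 sets two rounds for patients: "Patient Group (will be studied pre and 6 months after the surgery". For controls it says "Control group (will be studied only once expect brain fMRI", and the table lists a single raclopride/carfentanil visit. The only later control visit is "2. MRI-visit (after 6 months", and MRI is the only examination listed for it. The heading in section 6.1 is "Control group: (will be studied only once", over the same visit list.

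**The radiation dose.** Section 6.2 states that "the total dose accounting all PET-studies for patients is less than 22.5 mSv and for control group less than 11.25 mSv". Section 9.1 gives the reason: "As the control group is studied only once the radiotion dose will be around 11.25 mSv".

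**The budget.** Section 16 shows 100 studies for each receptor tracer. A separate line covers 20 control fMRI repeats at 6 months, with no PET counterpart.

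**The concern.** A two-by-two interaction asks whether the change over time differs between groups. It needs a change in each group. The protocol collects that change in patients but not in controls for either receptor tracer.

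Separating causes from consequences of obesity is the stated rationale for studying surgery patients alongside lean people (sections 1 and 2.4.2). The two neurotransmitter systems are objective 7 in section 3.1, and section 3.2.3 predicts the direction of change in each after weight loss. Section 6.4.6 is where the protocol says how reversibility will be tested, and the test it names cannot be run on the planned data.

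An analyst who follows the text must depart from it or supply the missing cell by assumption. The usual assumption, that controls would not have changed, yields a number that looks control-adjusted but is not.

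**Working it through.** **1. How many receptor scans do controls have?**

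Inputs: 40 patients and 20 controls (sections 5.1 and 12.1); 100 studies per tracer (section 16).

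- Controls scanned once: 40 × 2 + 20 × 1 = 100. This matches the budget.
- Controls scanned twice: 40 × 2 + 20 × 2 = 120. This does not.

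The budget row label is only partly legible (2x40 can be read), so the 20 control scans are inferred from the total. The visit tables settle the matter without it.

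**2. Does the radiation dose agree?**

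Inputs: mean effective dose per injection from Appendix 4 (water 1.0, FTHA 3.5, raclopride 2.0, carfentanil 1.4 mSv) and 6.7 mSv for CT.

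- One tracer round: 1.0 + 3.5 + 2.0 + 1.4 = 7.9 mSv.
- Two rounds plus CT: 2 × 7.9 + 6.7 = 22.5 mSv, the stated patient total.
- Half of that: 22.5 / 2 = 11.25 mSv, the stated control dose.

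The control dose is therefore that of one PET round. (The printed tracer subtotal of 14.8 mSv gives 14.8 + 6.7 = 21.5, not 22.5, whereas the per-injection doses sum to 15.8. Those figures need reconciling, but they do not bear on this point.)

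**3. Can the interaction be estimated?**

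Let G = 1 for obese and 0 for lean, T = 1 for the second measurement and 0 for the first, and let the mean be b0 + b1·G + b2·T + b3·G·T. The interaction is b3.

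| Cell | Subjects with a receptor scan | Mean |
|---|---|---|
| Lean, first | 20 | b0 |
| Obese, preoperative | 40 | b0 + b1 |
| Obese, postoperative | 40 | b0 + b1 + b2 + b3 |
| Lean, second | 0 | b0 + b2 |

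Written as cell means, b3 = (obese post − obese pre) − (lean second − lean first). The last bracket has no data.

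In the design matrix, every row with T = 1 belongs to a patient, so the T and G·T columns are identical. The matrix has 100 rows and rank 3 of 4. Neither b2 nor b3 is estimable; only b2 + b3 is, and that is the patients' pre/post change. With controls scanned twice there would be 120 rows and rank 4 of 4, and b3 would be estimable.

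**4. What if the missing cell is assumed?**

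Setting lean change to zero means b2 = 0. Then b3 = obese post − obese pre, the same quantity as the paired change. Nothing has been subtracted for time or retest effects.

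**5. What can be estimated from the planned scans?**

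- Obese preoperative − lean = b1.
- Obese postoperative − obese preoperative = b2 + b3.
- Obese postoperative − lean (single scan) = b1 + b2 + b3.

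**The case against.** The best reply is that little is lost. The baseline obese–lean gap, the within-patient change and the postoperative gap can all be had from scans already scheduled. Section 6.4.6 is headed as predictions, and an analyst would soon see that the interaction term is aliased. All of this is true, and it limits the harm to the missing correction for time and retest drift. It does not rescue the text, which names a specific test rather than leaving the choice open. A later analysis plan could follow it only by assuming the missing cell.

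Some stronger readings are tempting but not supported:

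- **That the main effect of group is diluted** by averaging patients' obese and weight-reduced states. Section 6.4.6 does not say that patients are averaged over the two measurements, and section 3.2.3 frames the hypothesis as obese versus lean. With group and measurement both in the model, three cell means are fitted by three parameters and the group term is the baseline gap. A loss of power would arise only if measurement were left out, which the protocol does not propose.
- **That controls must be dropped or their scan used twice.** A likelihood-based mixed model keeps all 60 subjects; it simply cannot fit the interaction column. The mixed ANOVA in section 6.3.2.2 belongs to fMRI, while section 6.2 names ROI-based statistics and SPM for receptor PET.
- **That no receptor hypothesis can be tested.** The correlation of food craving with MOR (section 6.4.6) and of BOLD response with D2R (section 6.4.5) need no second control scan.

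**Conclusion.** Wrong as written. The named test of D2R and MOR reversibility is not estimable, because 0 of 20 controls have a second receptor scan and the design has rank 3 of 4. The conclusion rests on the visit schedule alone. It needs no assumption about effect size, variance, correlation or dropout, and the dose and scan-count checks only corroborate it.

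The scope is narrow: the group-by-measurement interaction for the two receptor tracers. The obese–lean comparison at baseline stands, as does the paired change in patients. The fMRI group-by-time comparison also remains possible, because controls return for MRI at 6 months. What the design cannot give for receptor PET is a change in patients corrected for the change that lean subjects would show over the same interval.

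**What to change.** In section 6.4.6, remove the group-by-measurement interaction for D2R and MOR and specify instead:

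1. Preoperative patients (n=40) versus controls (n=20), one scan each, stated as the group comparison.
2. Paired pre/post change in the 40 patients, with randomised arm (20 and 20) as a between-subject factor.
3. Postoperative patients versus the same single control scans, reported as a residual difference with a 95% CI.

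Add a sentence saying that PET change is not corrected for time or test–retest drift. A group-by-time test can stay for fMRI. The section 6.1 heading for controls should also carry the fMRI exception found in section 4.2, since its own table lists the second MRI visit.

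The cost is protocol and analysis-plan wording only, with no added scans, radiation or visits. Keeping the interaction would require 20 more scans per tracer (120 instead of 100) and a further receptor PET visit for controls, which the stated control dose does not cover.

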### 6.4.7. Predictions: fMRI

We predict that in the preoperative scan, the patients will show elevated responses to high vs. lowcalorie foods in the reward circuit (ventral striatum, amygdala, medial prefrontal cortex). However, this hyperactivation predicted to be abolished after weight loss surgery. Regarding MOR and  $D_2R$ , we hypothesize that increased anticipatory reward activity (as indexed by fMRI) due to foods in the ventral striatum is associated with decreased striatal MOR and  $D_2R$  density.

### 6.4.8. Predictions: DTI and VBM

Prior to surgery, patients are expected to have lower GM and WM density in the regions related to reward processing including medial prefrontal cortex and striatum. If these differences in tissue composition are due to adiposity, they are expected to be abolished by the weight loss following the surgery. However, if they are markers of increased propensity for gaining weight, weight loss surgery will not have an effect on these regional differences. On the basis of prior PET studies(106) we predict that connectivity of the striatum and frontal cortical regions will be decreased in obese vs. lean individuals. Again, comparison of the postoperatively acquired tract skeletons reveals whether these changes are reversible.

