# 2.4.2. Obesity surgery as a novel way for studying the causes and consequences of obesity

Over the past decade, bariatric weight loss surgery has gained increasing acceptance as a treatment modality for morbid obesity. Bariatric surgery is a very effective means for weight loss among morbidly obese patients. Surgical treatment results in pronounced weight loss in short time and has also beneficial effects on co-morbid diseases (9). Obesity surgery also provides a novel methodological approach for studying whether specific brain-level differences between obese and lean individuals are causes or consequences of obesity. A longitudinal study on individuals undergoing obesity surgery allows us to assess whether the observed differences between obese and lean individuals are associated with the obese phenotype and are thus recoverable by the surgery, or whether they represent stable individual differences that constitute as risk factors which explain why some people become obese or addicted. Such dissociation has a major impact on the appropriate psychological and pharmacological treatment of obesity.

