### 3.2.2. The main hypotheses of MRI/MRS

We predict that the liver and mediastinal fat content is effectively decreased due to surgery.

Brain white matter volumes among obese are expected to be larger and to decrease during surgeryinduced weight loss. The bone marrow fat content should decrease upon surgery induced weight loss.

3.2.3. The main hypotheses of the brain activation studies (fMRI) and molecular imaging studies (neurotransmitter PET):

We predict that the neural responses of the reward circuit (amygdale, ventral striatal and midbrain regions) will be decreased post-operatively for the appetizing vs. bland foods in surgical groups. The differential activity is expected to be more profound in the patient group before surgery vs. healthy controls [54]. This between-groups difference in the activity of the reward system is expected to diminish in the post-operative scan. Furthermore, it is expected that this change in responsiveness is due to decreased responses to appetizing food only. In addition the changes of brain activation due to surgery-induced weight loss are expected to correlate with changes in gastrointestinal hormone secretion and with subjective feelings of hunger. Obesity is predicted to be associated with lowered grey and white matter volume (as measured by voxel-based morphometry), as well as altered connectivity between the subcomponents of the reward circuit (as measured by diffusion tensor imaging).

We predict that striatal  $D_2$  receptors, as measured with [C]raclopride, are decreased in obese individuals in comparison with lean control subject, and that weight loss following surgery results in increase in the number of these receptors. This would be consistent with lowered sensitivity to actual food reward in obesity. These receptors are also expected to predict functional responses in fMRI, especially receptors in the ventral striatum. Given the role of  $\mu$ -opioid receptors in reward functions, we predict that these receptors are increased in the brain reward network in obesity, consistent with hypersensitivity to anticipatory reward in obesity. Again, these receptors are hypothesized to correlate with fMRI responses – and with dopamine  $D_2$  receptors. Finally, we predict that weight loss will normalize the brain opioid dysfunction in obesity.

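### White matter volume in obesity is predicted in opposite directions, and an unreversed brain difference at 6 months cannot by itself separate a pre-existing trait from other explanations

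*Protocol*

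**What the plan says.** **White matter.** Section 3.2.2 (main hypotheses of MRI/MRS) states: "Brain white matter volumes among obese are expected to be larger and to decrease" with weight loss after surgery. Section 3.2.3 (main hypotheses of the fMRI and neurotransmitter PET studies) states: "Obesity is predicted to be associated with lowered grey and white matter volume", measured by voxel-based morphometry. Section 6.4.8 adds that before surgery "patients are expected to have lower GM and WM density in the regions related to reward processing".

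**Reading of the 6-month result.** Section 1 says that studying lean people and surgical patients allows the team to judge whether brain differences cause obesity or follow from it. Section 2.4.2 sets two alternatives: the differences belong to the obese state and recover with surgery, "or whether they represent stable individual differences that constitute as risk factors". Section 6.4.8 applies this to tissue composition. Differences due to adiposity should be abolished, but "if they are markers of increased propensity for gaining weight, weight loss surgery will not have an effect on these regional differences". None of these sections names a third possibility.

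**Opioid receptors (MOR).** Section 3.2.3 says "we predict that these receptors are increased in the brain reward network in obesity", and section 6.4.6 repeats this for the striatum. Section 6.4.7 says "we hypothesize that increased anticipatory reward activity (as indexed by fMRI) due to foods in the ventral striatum is associated with decreased striatal MOR".

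**Size and timing.** Section 12.1 gives 20 + 20 patients and 20 controls at alpha 0.05, without effect size, SD, power or sidedness. Patients are scanned before surgery and 6 months after (section 4.2).

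**The concern.** There are two separate problems.

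First, a main hypothesis should say which result would count against it. With white matter volume predicted both larger and smaller in the obese, a significant difference in either direction can be reported as predicted. The expected course after surgery is affected too: a fall is the prediction under 3.2.2, while a reversal under 3.2.3 and 6.4.8 would be a rise.

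Second, the two-way scheme treats failure to reverse as the mark of a stable risk factor. That does not follow. A trait would predict no change, but so would other states of affairs, and with 40 patients a real partial reversal can be missed. Section 2.4.2 says the distinction bears on how obesity should be treated psychologically and pharmacologically, so a wrong reading would reach beyond this study.

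**Working it through.** **1. The white matter statements side by side**

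| Section | Measure | Obese vs lean | After weight loss |
|---|---|---|---|
| 3.2.2 | Volume, no region named | Larger | Decrease |
| 3.2.3 | Volume (voxel-based morphometry), no region named | Lower | Not stated |
| 6.4.8 | Density in reward regions | Lower | Abolished if due to adiposity |

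A global-versus-regional distinction might reconcile 3.2.2 with 6.4.8. It cannot reconcile 3.2.2 with 3.2.3 as written, since both speak of volume and neither names a region.

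**2. Would adiposity be gone at 6 months?**

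The protocol gives no 6-month weight loss. Section 2.2 gives average excess weight losses at 1 year: 33-83% for sleeve gastrectomy and 60-85% for traditional operations. Section 2.1 puts normal weight below BMI 25. Assumptions: baseline BMI 40 or 45, reference BMI 25.

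BMI after = 25 + (1 − EWL) × (BMI before − 25)

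- BMI 40: 33% loss gives 25 + 0.67 × 15 = 35.05; 85% gives 25 + 0.15 × 15 = 27.25.
- BMI 45: 33% gives 25 + 0.67 × 20 = 38.4; 85% gives 25 + 0.15 × 20 = 28.0.

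The range is about 27 to 38. On these averages a difference caused wholly by adiposity need not have disappeared.

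**3. How large a change would be seen?**

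The stated sample size cannot be reproduced, because section 12.1 gives no effect size, SD, power or sidedness. Working backwards with a paired t-test, n = 40, two-sided 0.05, no dropout (noncentral t):

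- Change detectable with 80% power: 0.45 SD of the change scores.
- True change of 0.3 SD of the change scores: power 0.46, missed 54% of the time.
- True change of 0.2 SD: power 0.23, missed 77% of the time.

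These effect sizes are illustrative.

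**4. Dependence on the pre/post correlation**

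Assume a baseline gap of 0.5 between-subject SD, half of it reversed, so a true change of 0.25 SD. The SD of change is √(2(1 − ρ)) in between-subject SD units, and the standardised change is 0.25 / √(2(1 − ρ)).

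| ρ | SD of change | Standardised change | Missed, paired test, n = 40 | 95% CI half-width for mean change (between-subject SD) |
|---|---|---|---|---|
| 0.5 | 1.00 | 0.25 | 66% | 0.32 |
| 0.7 | 0.77 | 0.32 | 49% | 0.25 |
| 0.9 | 0.45 | 0.56 | 7% | 0.14 |

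With a gap of 0.8 SD and half reversed, the miss rates are 31%, 11% and under 1%. So the risk is serious for noisy measures or small gaps, and slight for very reproducible measures or large gaps.

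The last column shows why significance is the wrong criterion. Take the 0.5 SD gap as known and suppose the observed change is exactly zero. The interval would exclude a reversal of half the gap (0.25 SD) clearly at ρ = 0.9, only marginally at 0.7, and not at 0.5. All three results would be non-significant.

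**5. What an unreversed difference is compatible with**

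(a) A pre-existing trait; (b) residual adiposity at 6 months; (c) a slow or permanent consequence of past obesity; (d) a real reversal too small to detect. The protocol's scheme names only (a). Precision can rule out (d), and relating brain change to BMI change bears on (b). Nothing in a before-and-after surgical design separates (a) from (c).

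**The case against.** A reader might infer that the brain predictions conflict generally, so that no result could refute the study's claim. The protocol does not support that. Grey matter (lower), D2 receptors (lower, then rising), fMRI response to appetising food (higher, then abolished) and fronto-striatal connectivity (decreased in 6.4.8) each have one direction. Persistent fMRI hyperactivation, for example, would contradict section 6.4.7. A clear reversal would count against the trait reading, and a precise absence of change in patients who lost much weight would count against the adiposity reading.

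A reader might also call the MOR statements contradictory. They are not. Higher MOR in the obese is a group difference; the negative link with fMRI activity in 6.4.7 is an association, and the two may differ in sign. What remains is a tension in rationale, since 3.2.3 explains the increase by saying that "these receptors are increased in the brain reward network in obesity, consistent with hypersensitivity to anticipatory reward in obesity".

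Third, section 6.4.8 reasons forward from hypothesis to prediction. It does not state that a non-significant test proves a trait, its last sentence asks only about reversibility, and section 6.4.6 refers to successful weight loss. It would go too far to say that every missed change will be reported as a trait. Margins and interval rules may also properly sit in a statistical analysis plan that is not at hand. This stands as far as it goes. But sections 1 and 2.4.2 present the alternatives as exhaustive, and an analysis plan would not remove that framing or the white matter contradiction.

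Finally, the numbers rest on chosen inputs. Controls may have a BMI up to 27 (section 5.2), so 25 is not the comparison group's upper limit, and for the receptor studies section 6.4.6 names a group-by-measurement interaction rather than a paired test. Both are fair limits on the illustration.

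**Conclusion.** The point holds in two limited parts.

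- **White matter direction:** a plain contradiction between sections 3.2.2 and 3.2.3, with 6.4.8 on the side of lower. It needs no assumption and must be reconciled.
- **Reading of the 6-month result:** the two-way scheme is incomplete. An unreversed or non-significant change cannot separate a trait from residual adiposity, a lasting consequence of obesity or imprecision.

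The sizes are illustrative. Residual BMI of about 27-38 assumes baseline 40-45, reference 25 and 1-year averages standing in for 6 months. The 0.45 SD detectable change and the 54% miss rate at 0.3 SD assume a paired test, 40 complete pairs and two-sided 0.05, on the scale of the change scores. For half-reversal of a 0.5 SD gap the miss rate runs from 66% to 7% as the pre/post correlation goes from 0.5 to 0.9, so no single figure should be quoted as the study's error rate. Dropout would raise all of them. The matter should be corrected, but it does not undermine the other directional brain hypotheses.

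**What to change.** 1. Give white matter one direction across 3.2.2, 3.2.3 and 6.4.8. Alternatively, state that global volume and regional density are separate hypotheses, each with its own direction, or declare the comparison non-directional and two-sided.
2. For each brain measure, report the pre/post change in patients and the residual patient-control difference, both with 95% confidence intervals.
3. Regress brain change on BMI change. Section 6.7 already has BMI measured at every time point.
4. Replace the two-way reading in 2.4.2 and 6.4.8 with three conclusions: reversed; not reversed at 6 months, used only if the confidence interval excludes reversal of a pre-set share of the baseline gap; and inconclusive. The investigators should choose that share in advance. State that a pre-existing trait will not be inferred from a non-significant change.
5. Optionally, add a sentence on how higher MOR in obesity (3.2.3, 6.4.6) fits with the negative association in 6.4.7.

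The cost is protocol or analysis plan wording and one regression on data already planned, with no extra scans or patients. The real price is weaker causal language about what makes people vulnerable to obesity.
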